#### 6.6.2. Other Safety Summaries

For laboratory tests, 12-lead ECG parameters and vital signs, summaries include categorical tables (e.g., normal, high, low), and descriptive statistics for change from baseline by treatment group and visit. For the fluorescence-activated cell sorting (FACS), the endpoints to be summarized, which are subsets of lymphocytes and are measured at baseline, Month 3, and Month 6/early termination, are as follows: CD3 + (%, abs), CD3 + CD4 + (%, abs), CD3 + CD8 + (%, abs), CD19 + (%, abs), CD16 + /CD56 + (%, abs). Raw values as well as percent change from baseline will be summarized with descriptive statistics by treatment group and visit.

Demographic parameters will be summarized (as number and percent or mean, standard deviation, and range) by treatment group and gender following CaPS.

The number and percent of subjects reporting specific past and present medical histories at screening will be summarized by medical history reporting term (from the Medical Dictionary for Regulatory Activities (MedDRA)) and treatment group following CaPS.

Clinical findings on any physical examination during the study will be tabulated by treatment group following CaPS.

Previous and concomitant mediation usage by medication type will be tabulated by treatment group using the WHO-Drug dictionary following CaPS.

#### 6.7. Additional Analyses to Address COVID-19 Pandemic Impacts

#### 6.7.1. Additional Supportive Analysis of the Primary Endpoint

The analysis of ACR50 response rate at Month 3 described in Section 6.1.1.1 will also be conducted by excluding subjects with ACR50 response at Month 3 missing due to COVID-19 pandemic impact or with ACR50 components collected remotely during COVID-19 pandemic. This will serve as an additional supportive analysis of the primary endpoint.

Endpoint: ACR50 response rate at Month 3

- Analysis time points: Month 3
- Analysis population: FAS excluding subjects impacted by COVID-19 pandemic (i.e., excluding subjects with missing or remote Month 3 visit due to COVID-19 pandemic, or any PD due to COVID-19 pandemic that had an impact on the primary endpoint)
- Method of imputation for missing data: MR=NR (specified in Section 5.3)
- Analysis methodology: Normal approximation (specified in Section 5.2.1.1).

#### **Reporting results:**

- Response rate with imputation: N, frequency and percentage of responders, SE of the response rate at Month 3 will be presented by treatment group.
- Response rate difference with imputation: Difference between treatment groups, and corresponding SE, 95% CI and p-value at Month 3 will be presented.
- A listing of subjects who were impacted by COVID-19 pandemic and excluded from this additional supportive analysis.

### 6.7.2. Other Summaries and Listings Depicting COVID-19 Pandemic Impacts

- An anchor date will be used as a start date for COVID-19 pandemic related periods in analyses. For China, the date COVID-19 was identified as the causative agent of outbreak in Wuhan by the China Center for Disease Control and Prevention (January 9, 2020) will be used as the anchor date for COVID-19 pandemic.
- A summary table showing visits attended both before and after the anchor date will be produced. Visit attendance will be based on swollen joint count data.
- A summary table of number of subjects with major impact by COVID-19 pandemic, which includes:
  - Subjects who were excluded from the additional supportive analysis in Section 6.7.1.
  - Subjects who withdraw from the study due to COVID-19 pandemic before Month 3.
- Protocol deviations related to COVID-19 pandemic will be summarized and listed separately. Both important and non-important PDs related to COVID-19 pandemic will be reported.
- A separate summary table solely for subject discontinuations related to COVID-19 pandemic, if any, will be provided.
- COVID-19 related AEs, if any, will be reported separately.
- A summary table showing AEs reported both before and after the anchor date will be produced by treatment group. This summary will consider windows of equal duration before and after the anchor date.
- Data collected remotely during COVID-19 pandemic for PROs and laboratory tests will be marked and footnoted in corresponding listings.

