# 6.2.7. Visit 7, Month 6, Day 169 or Early Termination Visit

There is a  $\pm 7$  day window for the Month 6 visit.

**Subjects are required to fast for at least 9 hours prior to the visit.** Blood collection may be taken up to 48 hours following this visit as necessary to ensure samples are collected in a fasted state.

All PROs should be completed prior to any other study procedures. These include the following:

- Patient's Assessment of Arthritis Pain (VAS);
- Patient's Global Assessment of Arthritis (VAS);
- HAQ-DI;
- SF-36 Version 2 (Acute);
- EQ-5D;
- WPAI-PsA.

- Vital signs: blood pressure, pulse rate and temperature (tympanic, oral or temporal preferred);
- Risk factor check for venous thromboembolism (see Section 7.5.8);
- Laboratory testing: Hematology, Chemistry Panel, CRP, HbA1c, Lipid Panel (fasting), Urinalysis; Lymphocyte subset analysis (FACS), Urine Pregnancy Test (for women of childbearing potential only);
- Contraception check: Confirm and document that proper contraception is being used;
- Complete Physical Examination: weight, general appearance, skin (presence of rash), HEENT (head, eyes, ears, nose and throat), lungs (auscultation), heart (auscultation for presence of murmurs, gallops, rubs), extremity exam (presence of peripheral edema), abdomen (palpation and auscultation), neurologic (mental status, station, gait, reflexes, motor and sensory function, coordination) and lymph nodes;
- Waist and hips circumference;
- 12-lead electrocardiogram.

- Clinical Evaluation of Rheumatology Endpoints (by blinded assessor):
  - Tender/Painful Joint Counts (68);
  - Swollen Joint Count (66);
  - Physician's Global Assessment of Arthritis (VAS);
  - Assessment of dactylitis using DSS;
  - Assessment of enthesitis using Leed's Index.
- Clinical Evaluation of Dermatology Endpoints (by blinded assessor):
  - PGA-PsO;
  - PASI;
  - BSA;
  - NAPSI;
  - Clinical Evaluation of Rheumatology and Dermatology Endpoint (by blinded assessor): PGA-PsA,
- Monitoring of adverse events and concomitant medications. Record any modifications, deletions or additions;
- Dosing diary check and Drug accountability;
- Review subject laboratory abnormalities to assess need for potential additional safety follow-up.

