## 8.1.4. Time Period for Collecting AE/SAE Information

The time period for actively eliciting and collecting AEs and SAEs ("active collection period") for each subject begins from the time the subject provides informed consent, which is obtained before the subject's participation in the study (ie, before undergoing any study-related procedure and/or receiving investigational product), through and including a minimum of 28 calendar days after the last administration of the investigational product.

For subjects who are screen failures, the active collection period ends when screen failure status is determined.

Medical occurrences that begin before the start of study intervention but after obtaining informed consent will be recorded on the Medical History/Current Medical Conditions section of the case report form (CRF), not the AE section.

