#### 9.1. Sample Size Determination

The sample size and power analysis for the primary endpoint are based on the randomization of approximately 204 subjects in a 2:1 ratio. The sample size for this study is driven by the ACR50 response rate.

Assuming a placebo response rate of 9.5% and factoring in the number of subjects with primary endpoint missing due to COVID-19 (around 11 subjects as of 29 May 2020), a sample size of approximately 204 Chinese subjects (approximately 136 subjects in the tofacitinib treatment arm and 68 subjects in the placebo arm) randomized in a 2:1 ratio to tofacitinib and placebo arms will yield at least 90% power to detect a difference of 18.5% from placebo in ACR50 response rate, based on normal approximation (without continuity correction) at the 2-sided 5% significance level.

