## **1. VERSION HISTORY**

SAP Version	Associated Protocol Amendment	Change	Rationale
1 (17-APR-2018)	Protocol Amendment 1 (20-NOV-2017)	None	Not Applicable
2 (22-FEB-2021)	Protocol Amendment 4 (04-JUN-2020)	Sections 2.2 and 5.3: Protocol languages were updated	To be consistent with protocol amendment 4.
		Section 3.4.3: Added details for prior DMARDs use summaries.	To clarify how prior DMARDs use will be summarized.
		Section 4.2.1: Added one additional criterion for subject exclusion from Per- Protocol analysis set.	To exclude subjects with history of or current autoimmune rheumatic disease or rheumatic inflammatory disease other than PsA.
		Sections 5.2 and 5.2.1.1: Updated method for reporting response rate when the rate is 0 or 100%.	To clarify the reporting method.
		Section 6.1.1.2 and Appendix 1: Sensitivity analysis in the per-protocol analysis set is renamed a supportive analysis.	Sensitivity analysis is reserved for a different statistical method but otherwise everything else (including the analysis set and missing data handling method) stays the same.
		Sections 6.2.1 and 6.2.2: Line graph will	For TLF reduction.

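### The before/after COVID-19 adverse event table in SAP 6.7.2 is standardised only by window length, so its counts may move with enrolment while the event rate stays the same

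*SAP*

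**What the plan says.** SAP 6.7.2 (Other Summaries and Listings Depicting COVID-19 Pandemic Impacts) fixes one calendar date for all subjects, the date on which the virus was identified by the "China Center for Disease Control and Prevention (January 9, 2020) will be used as the anchor date for COVID-19 pandemic". It then plans: "A summary table showing AEs reported both before and after the anchor date will be produced by treatment group". The one rule on comparability is: "This summary will consider windows of equal duration before and after the anchor date".

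The section does not give the length of the windows. It does not say whether they are set once for the study or separately for each subject, whether the entries are events or subjects, or what the denominator is. Nothing elsewhere fills the gap. SAP 5.2.3 and 6.6.1 describe adverse event displays as numbers, percentages and incidence, and no exposure-adjusted event rate appears anywhere in the SAP.

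Two protocol provisions set how long one subject can contribute events. Treatment runs to "Visit 7, Month 6, Day 169 or Early Termination Visit" (Protocol 6.2.7), and Protocol 8.1.4 continues collection "through and including a minimum of 28 calendar days after the last administration of the investigational product".

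**The concern.** Equal window length looks like a fair standardisation, but what governs the expected number of events is subject-time under collection. In a trial with staggered entry and fixed follow-up, the number of subjects on study on a given date depends on who entered in the preceding 28 weeks or so. Two windows of the same length hold the same subject-time only if the accrual feeding them was the same.

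The trial was running on both sides of the date. Protocol 9.1 counts about 11 subjects with a primary endpoint lost to COVID-19 by 29 May 2020. Amendment 4, dated 4 June 2020, raised the target from about 195 to about 204, so enrolment had evidently not closed five months after the date (an inference). Protocol 7.7 also provides for discontinuations caused by the pandemic, which can shorten subject-time on the later side only.

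The section title says that these displays depict pandemic impact. Without a denominator, a fall in events after January 2020 could be read as under-reporting, or a rise as an excess, when only the number of subjects on study has changed.

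**Working it through.** The SAP states no figure here to reproduce. The check asks how far subject-time can differ between windows of equal length.

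**Inputs from the documents.** Anchor date 9 January 2020 (SAP 6.7.2); 204 subjects (Protocol 9.1); about 168 days of treatment (Protocol 6.2.7) plus the minimum 28 days (Protocol 8.1.4), so 168 + 28 = 196 days of event collection per completer.

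**Inputs assumed, because the documents do not give them.** Even daily entry starting 1 June 2018, 1 October 2018 or 1 March 2019 and ending 30 June or 15 August 2020, with or without an enrolment pause from 25 January to 10 April 2020; no dropout; window length of 90 days, 180 days, or the time from the anchor to last follow-up (173 + 196 = 369 days or 219 + 196 = 415 days).

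**Formula.** A subject whose first dose is on day x (anchor = day 0) adds max(0, min(x + 196, b) − max(x, a)) days to a window from a to b. These are summed over the 204 subjects for (−L, 0) and (0, L). At a constant event rate, the ratio of expected counts equals the ratio of these sums.

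**Before/after subject-time ratio, no pause / pause:**

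| Entry start | Entry end | L = 90 | L = 180 | L to last follow-up |
|---|---|---|---|---|
| Jun 2018 | 30 Jun 2020 | 1.00 / 1.19 | 1.00 / 1.38 | 1.36 / 1.90 |
| Jun 2018 | 15 Aug 2020 | 1.00 / 1.19 | 1.00 / 1.38 | 1.30 / 1.72 |
| Oct 2018 | 30 Jun 2020 | 1.00 / 1.19 | 1.00 / 1.38 | 1.27 / 1.77 |
| Oct 2018 | 15 Aug 2020 | 1.00 / 1.19 | 1.00 / 1.38 | 1.14 / 1.50 |
| Mar 2019 | 30 Jun 2020 | 1.00 / 1.19 | 0.95 / 1.31 | 0.80 / 1.11 |
| Mar 2019 | 15 Aug 2020 | 1.00 / 1.19 | 0.95 / 1.31 | 0.68 / 0.90 |

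One cell in full: entry from June 2018 to 30 June 2020 with the pause and 180-day windows gives 28.8 subject-years before and 20.9 after, and 28.8 / 20.9 = 1.38. At an illustrative 1 event per subject-year, the expected count falls from 28.8 to 20.9 while the rate is 1.00 in both windows.

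**As apparent change in the later count (1/ratio − 1).** For 90 days, 0% to 1/1.19 − 1 = −16%. For 180 days, from 1/1.38 − 1 = −28% to 1/0.95 − 1 = +5%. For windows to last follow-up, from 1/1.90 − 1 = −47% to 1/0.68 − 1 = +47%. The longest windows differ even without a pause because the later one includes a tail in which nobody enters.

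**Percentages instead of counts.** A second set of assumed patterns (entry from 540 days before to 340 days after the anchor unless stated, 197 days per subject, constant hazard 0.01 per day, 180-day windows) compares subject-years with the percentage of subjects at risk who have an event:

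| Accrual | Subject-years before / after | Ratio | % of at-risk subjects before / after |
|---|---|---|---|
| Level | 22.5 / 22.5 | 1.00 | 55 / 55 |
| 90-day pause from day 14 | 25.1 / 17.3 | 1.45 | 55 / 51 |
| Linear ramp-up | 18.0 / 27.2 | 0.66 | 55 / 55 |
| Declining | 27.0 / 17.8 | 1.52 | 55 / 55 |
| Start 150 days before | 12.9 / 39.2 | 0.33 | 48 / 60 |

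A percentage of those at risk removes much of the distortion, though not always all of it. A percentage of all 204 would move much as the counts do. Steeper accrual patterns go outside the ranges in the first table, so those ranges are illustrations and not bounds.

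**The case against.** The strongest reply is that the documents show no imbalance. They contain no enrolment dates and no subject-time, level accrual gives a ratio of exactly 1.00, and the twelve-scenario set itself includes 1.00 for 90- and 180-day windows. A reader might infer that subject-time does differ across the date and that event reporting will therefore appear to change. The documents support neither statement, only that it can differ and that counts may move. This objection stands in full.

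Second, the SAP does not use the word calendar. Study-wide windows are the natural reading of a single fixed date, but windows set per subject are not ruled out, and they would largely remove the problem. That also stands, and the ambiguity is itself worth resolving.

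Third, a reader might infer that the placebo row would mix placebo time with tofacitinib time after the Month 3 switch. Existing conventions tell against this. SAP 5.2 relabels Sequence B after Month 3, SAP 6.6.1 separates treatment groups (to Month 3) from treatment sequence groups (to Month 6), and Appendix 2 counts new events on the switch day with Month 4 onward. What is left is a missing cross-reference in 6.7.2.

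Fourth, both arms share the same accrual calendar, so a comparison between arms inside one window is not distorted by accrual. This is correct. The point concerns only the comparison of one window with the other, which is what the table is laid out to show.

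Finally, the table carries no test or decision rule, and SAP 6.6.1 describes safety analysis as generally exploratory. That limits the weight of the point without removing it.

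**Conclusion.** The point holds in a limited form. The equal-length rule is the only standardisation in the SAP's before/after adverse event table, and with staggered entry it does not guarantee equal subject-time. Counts, and less so percentages, may therefore change across 9 January 2020 at a constant event rate.

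Size and direction cannot be derived from the documents. The illustrative ranges in the working rest on assumed accrual and on the study-wide reading of the windows, and they widen with window length, which the SAP leaves open. With short windows and level accrual there is no distortion.

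Priority is low. The table is descriptive, and neither the primary analysis nor the main adverse event displays (Baseline to Month 3 and Baseline to Month 6) depends on it. A change is still worthwhile because a better method is available at little cost.

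**What to change.** In SAP 6.7.2:

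- State the window length, and whether windows are defined for the study or for each subject.
- For each window and treatment label, report the number of subjects at risk and the subject-years under adverse event collection, from first dose to end of follow-up and cut at the window limits.
- Give events, and subjects with events, per 100 subject-years.
- Apply the labels already defined in SAP 5.2 and Appendix 2: placebo to Month 3, Sequence A tofacitinib, and Sequence B tofacitinib after the switch.

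With subject-years as the denominator, a constant event rate gives a rate ratio of 1.00 whatever the accrual, and the windows no longer need to be of equal length.

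The cost is a few lines of SAP text and one programmed denominator from dosing, switch and follow-up dates that are already collected. No other analysis changes.

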#### 7. INTERIM ANALYSES

There is no interim analysis planned for this study.

#### 7.1. Introduction

Not applicable.

#### 7.2. Interim Analyses and Summaries

Not applicable.

### **9. APPENDICES**

## Appendix 1. SUMMARY OF EFFICACY ANALYSES

Endpoint	Analysis Set	Analysis Timepoint	Statistical Method	Model	Missing Data Imputation	Interpretation
ACR50 Response Rate	FAS	Month 3	Normal approximation		MR=NR	Primary
ACR50 Response Rate	PP	Month 3	Normal approximation		MR=NR	Supportive Analysis
ACR50 Response Rate	FAS excluding subjects impacted by COVID-19 pandemic	Month 3	Normal approximation		MR=NR	Supportive Analysis
ACR50 Response Rate	FAS	Week 2, Months 1, 2, and 3	GMMRM	Fixed effects: treatment, visit, treatment*visit	None	Supportive Analysis
ACR50 Response Rate	FAS	Week 2, Months 1, 2, and 3	Tipping point analysis	Imputation model: Fixed effects: treatment, visit, treatment*visit	Multiple Imputation	Supportive Analysis
ACR50 Response Rate	Each defined category of each subgroup on FAS (see Section 6.4)	Month 3	Normal approximation		MR=NR	Subset Analysis
ACR50 Response Rate	FAS	Week 2, Months 1, 2, 4 and 6	Normal approximation		MR=NR	Secondary

ACR20 Response Rate	FAS	Week 2, Months 1, 2, 3, 4, and 6	Normal approximation	MR=NR	Secondary
ACR70 Response Rate	FAS	Week 2, Months 1, 2, 3, 4 and 6	Normal approximation	MR=NR	Secondary
$\Delta$ HAQ-DI (decrease) $\geq 0.30$ response rate	Subjects in FAS with baseline $HAQ-DI \ge 0.30$	Week 2, Months 1, 2, 3, 4 and 6	Normal approximation	MR=NR	Secondary
$\Delta$ HAQ-DI (decrease) $\geq 0.35$ response rate	Subjects in FAS with baseline $HAQ-DI \ge 0.35$	Week 2, Months 1, 2, 3, 4 and 6	Normal approximation	MR=NR	Secondary
PsARC response rate	FAS	Week 2, Months 1, 2, 3, 4 and 6	Normal approximation	MR=NR	Secondary
PGA-PsO response rate	Subjects in FAS with baseline $PGA-PsO \ge 2$	Months 1, 3, 6	Normal approximation	MR=NR	Secondary
PASI75 response rate	Subjects in FAS with baseline BSA $\geq 3\%$ and baseline PASI > 0	Months 1, 3, 6	Normal approximation	MR=NR	Secondary
Resolution of dactylitis	Subjects in FAS with baseline DSS > 0	Months 1, 3, 6	Normal approximation	MR=NR	Secondary
Resolution of enthesitis	Subjects in FAS with baseline LEI > 0	Months 1, 3, 6	Normal approximation	MR=NR	Secondary

ΔHAQ-DI	FAS	Week 2, Months 1, 2, 3, 4 and 6	MMRM	Fixed effects: treatment, visit, treatment*visit, baseline value	None	Secondary
ΔCRP	FAS	Week 2, Months 1, 2, 3, 4 and 6	MMRM	Fixed effects: treatment, visit, treatment*visit, baseline value	None	Secondary
Δ in Patient's Assessment of Arthritis Pain	FAS	Week 2, Months 1, 2, 3, 4 and 6	MMRM	Fixed effects: treatment, visit, treatment*visit, baseline value	None	Secondary
∆ in Patient's Global Assessment of Arthritis	FAS	Week 2, Months 1, 2, 3, 4 and 6	MMRM	Fixed effects: treatment, visit, treatment*visit, baseline value	None	Secondary
∆ in Physician's Global Assessment of Arthritis	FAS	Week 2, Months 1, 2, 3, 4 and 6	MMRM	Fixed effects: treatment, visit, treatment*visit, baseline value	None	Secondary
$\Delta$ in swollen joint count	FAS	Week 2, Months 1, 2, 3, 4 and 6	MMRM	Fixed effects: treatment, visit, treatment*visit, baseline value	None	Secondary
$\Delta$ in tender/painful joint count	FAS	Week 2, Months 1, 2, 3, 4 and 6	MMRM	Fixed effects: treatment, visit, treatment*visit, baseline value	None	Secondary

ΔPGA-PsO	Subjects in FAS with baseline PGA-PsO > 0	Months 1, 3, 6	MMRM	Fixed effects: treatment, visit, treatment*visit, baseline value	None	Secondary
ΔDSS	Subjects in FAS with baseline DSS > 0	Months 1, 3, 6	MMRM	Fixed effects: treatment, visit, treatment*visit, baseline value	None	Secondary
ΔLEI	Subjects in FAS with baseline LEI > 0	Months 1, 3, 6	MMRM	Fixed effects: treatment, visit, treatment*visit, baseline value	None	Secondary
$\Delta$ SF-36v2 (10 endpoints)	FAS	Months 1, 3, 6	MMRM	Fixed effects: treatment, visit, treatment*visit, baseline value	None	Secondary
ΔEQ-5D (5 endpoints) and EQ-VAS	FAS	Months 1, 3, 6	MMRM	Fixed effects: treatment, visit, treatment*visit, baseline value	None	Secondary
ΔDAS28-3(CRP)	FAS	Week 2, Months 1, 2, 3, 4 and 6	MMRM	Fixed effects: treatment, visit, treatment*visit, baseline value	None	Other
ΔPGA-PsA	FAS	Months 1, 3, 6	MMRM	Fixed effects: treatment, visit, treatment*visit, baseline value	None	Other

%Δ in PASI and PASI clinical sign component scores	Subjects in FAS with baseline BSA $\geq 3\%$ and baseline PASI > 0	Months 1, 3, 6	MMRM	Fixed effects: treatment, visit, treatment*visit, baseline value	None	Other
%ΔBSA	Subjects in FAS with baseline BSA > 0%	Months 1, 3, 6	MMRM	Fixed effects: treatment, visit, treatment*visit, baseline value	None	Other
ΔΝΑΡSΙ	Subjects in FAS with baseline NAPSI > 0	Months 1, 3, 6	MMRM	Fixed effects: treatment, visit, treatment*visit, baseline value	None	Other
ΔWPAI-PsA	FAS	Month 3 & Month 6	MMRM	Fixed effects: treatment, visit, treatment*visit, baseline value	None	Other

## Appendix 2. DEFINITION AND USE OF VISIT WINDOWS IN REPORTING

For reporting purposes, the following visit windows will be used for efficacy/PRO variables and for any safety displays that display by week/month. All observations regardless of on- or off-treatment will be used. For an endpoint that consists of multiple components, e.g., ACR50 and DAS28-3(CRP), the components should be collapsed first in the same visit window to derive the endpoint.

If two or more visits/observations fall into the same window, the visit/observation closest to the target day will be used in the analyses. If there is a tie, the later visit/observation will be used. However, for a subject who discontinues from the study early prior to the Month 6 visit and who does not have an observation within the Month 6 visit window, if two or more observations fall in the same visit window (i.e., a visit window prior to Month 6), then the latest observation (rather than the observation closest to the target day) within this visit window will be used in the analysis for that visit window.

Visit Label	Target Day	Definition [Day Window]
Screening		< Day 1
Baseline	Day 1	Last non-missing assessment on or before Day 1 and prior to first dose of study drug administration
Week 2	Day 15	Day 2 to Day 21
Month 1	Day 29	Day 22 to Day 42
Month 2	Day 57	Day 43 to Day 70
Month 3	Day 85	Day 71 to [Treatment Switch Day or Day 98, whichever is smaller]
Month 4	Day 113	[Treatment Switch Day + 1 or Day 99, whichever is smaller] to Day 140
Month 6	Day 169	≥ Day 141

Target day is equal to the target week  $\times$  7 days + 1 day. A month is 4 weeks or 28 days.

Treatment Switch Day = date of the first dose of treatment switch at month 3 (i.e., treatment switch date – date of the first dose + 1). The first dose of the treatment switch at Month 3 will be taken from the first dosing date from the Month 4 oral dosing CRF.

All the data collected on the treatment switch day will be counted in  $\leq$  Month 3 except for the AE data. Any new treatment emergent AE occurred on the day of treatment switch will be counted in  $\geq$  Month 4.

Note that the upper limit of the Month 3 visit window and the lower limit of the Month 4 visit window are defined for each of ALL the subjects in the study since, per the study protocol, subjects randomized to the placebo group will receive tofacitinib 5 mg BID in a blinded fashion for the remainder of the study. Further details for the Month 3/Month 4 visit windows are in order.

PFIZER CONFIDENTIAL Page 41

- 1. If Treatment Switch Day falls between Day 71 and Day 98, then the upper limit of the Month 3 visit window is the smaller of Treatment Switch Day or Day 98 and the lower limit of the Month 4 visit window is the smaller of Treatment Switch Day + 1 or Day 99;
- 2. If Treatment Switch Day is < 71, > 98, or missing, the upper limit of the Month 3 visit window will be Day 98 and lower limit of the Month 4 visit window will be Day 99.

If Treatment Switch Day is < 71 71-98 > 98 Missing Visit label Month 3 Month 4 Month 4 Month 3 Month 4 Month 3 Month 3 Month 4 Day Window 71 to 98 99 to 140 71 to 98 99 to 140 71 to 98 99 to 140 from from [72 to 140] [71 to 71] up to up to [71 to 98] [99 to 140]

Effects of Bullets 1 and 2 above are further illustrated as follows.

The visit window definitions will be applied to all the endpoints, such as efficacy, PRO, safety etc. Note some of the endpoints may not be measured at every visit. For example, dactylitis will be assessed at baseline, Months 1, 3, and 6, and visit windows at Week 2, Months 2 and 4 will be undefined. In the event that an observation may fall into one of the undefined visit windows, that observation will not be used in analysis.

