#### 4.3. Safety Analysis Set

The safety analysis set (SAFETY) will include all subjects who received at least one dose of the study drug (tofacitinib or placebo). Subjects will be classified according to the actual study treatment received.

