### 5.2. General Methods

As subjects randomized to treatment group of placebo  $\rightarrow$  tofacitinib 5 mg BID (where  $\rightarrow$  means switching to) will advance from placebo to open-label treatment of tofacitinib 5 mg BID at Month 3, the treatment label used for reporting visits up to Month 3 will be "Placebo" and treatment label for reporting visits after Month 3 through Month 6 will be "Placebo  $\rightarrow$  Tofacitinib 5 mg BID".

For analyses through Month 3, the following treatment comparison will be made at each time point, where applicable:

• Tofacitinib 5 mg BID vs. Placebo.

For analyses after Month 3 through Month 6, the following treatment comparison will be made at each time point,

• Tofacitinib 5 mg BID vs. Placebo  $\rightarrow$  Tofacitinib 5 mg BID.

The primary efficacy comparison for the primary endpoint of ACR50 will be between tofacitinib 5 mg BID and placebo at Month 3.

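### For subjects who stop early, the SAP visit windows can report off-drug follow-up laboratory values as Month 2, 3, 4 or 6 and, after Month 3, can leave the Early Termination value out of every by-visit row

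*SAP*

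**What the plan says.** SAP Appendix 2 sets day windows for efficacy and patient-reported variables and for safety displays organised by week or month. It adds that "The visit window definitions will be applied to all the endpoints, such as efficacy, PRO, safety etc" and that "All observations regardless of on- or off-treatment will be used". The last window, Month 6, starts at Day 141 and has no upper limit. There is no Follow-up label.

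Within a window, the value closest to the target day is used, and a tie goes to the later value. There is one exception. For a subject who leaves early and "who does not have an observation within the Month 6 visit window", the latest value in an earlier window is used instead.

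The border between Month 3 and Month 4 depends on the treatment switch day, whose date "will be taken from the first dosing date from the Month 4 oral dosing CRF". If that day is outside Days 71 to 98 "or missing, the upper limit of the Month 3 visit window will be Day 98". For tests not scheduled at a visit: "In the event that an observation may fall into one of the undefined visit windows, that observation will not be used in analysis".

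Protocol 6.2.8 requires a Follow-up Visit with haematology, chemistry and lipids, 28 to 42 days after the last dose, for subjects who stop because of an adverse event or a qualifying laboratory abnormality. Abnormalities still present then are followed further, and Protocol 6.3.2 asks for monthly creatinine retests until the value is stable. SAP 6.6.2 summarises laboratory change from baseline by treatment group and visit.

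**The concern.** The exception for early leavers selects a subject's last value, which without a follow-up test is the Early Termination value. A follow-up value can defeat it in two ways. If it falls in the same window, it is now the latest value and replaces Early Termination. If it falls on Day 141 or later, the subject has a Month 6 observation, so the exception no longer applies.

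The subjects with a mandatory follow-up test after stopping early are those who stopped for safety reasons. Protocol 1.2.5 gives a half-life of about 3 hours, so a value four to six weeks after the last dose is off drug. Protocol 1.2.4.2 says falls in blood counts usually resolved after stopping, and Protocol 9.4 singles out these and related laboratory measures. A by-visit table could therefore show a recovered value for a subject whose value at stopping was abnormal.

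**Working it through.** **The plan's own figures.** Target days 15, 29, 57, 85, 113 and 169 are week × 7 + 1 for weeks 2, 4, 8, 12, 16 and 24. The window starts are the midpoints: (15+29)/2 = 22, (29+57)/2 = 43, (57+85)/2 = 71, (85+113)/2 = 99, (113+169)/2 = 141. These match Appendix 2.

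**Assumptions.** Scheduled haematology and chemistry on target days; Early Termination (ET) on the last-dose day L; follow-up at L + 28 or L + 42; switch on Day 85. Possible stop days after Month 3 are L = 86 to 168, which is 83 days.

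**Switch day known, follow-up at +28.**
- L = 86–112 (27 days): follow-up on Days 114–140 shares the Month 4 window with ET. There is no Month 6 value, so the latest is used: follow-up.
- L = 113: ET is itself the Day 113 value and is kept.
- L = 114–140 (27 days): follow-up on Days 142–168 is reported as Month 6. The exception is off, Month 4 keeps the Day 113 value, and ET is in no row.
- L = 141–155 (15 days): both fall in Month 6. At L = 155 the distances are 169 − 155 = 14 and 183 − 169 = 14, and the tie goes to follow-up.
- L ≥ 156: ET is closer (13 against 15 at L = 156) and is kept.

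**Switch day known, follow-up at +42.**
- L = 86–98 (13 days): follow-up replaces ET in Month 4.
- L = 99–112: follow-up is reported as Month 6; ET is alone in Month 4 and is kept.
- L = 114–140 (27 days): as above, ET is in no row.
- L = 141–148 (8 days): follow-up replaces ET in Month 6 (tie of 21 and 21 at L = 148).
- L ≥ 149: ET is kept (20 against 22 at L = 149).

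**Switch day missing for stops before the Month 4 visit.** Month 3 then runs to Day 98, so stops on Days 86–98 keep ET as the latest Month 3 value.

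| Days on which ET is in no row (of 83) | +28 | +42 |
|---|---|---|
| Switch known: replaced in the same row | 27 + 15 = 42 | 13 + 8 = 21 |
| Switch known: Month 4 shows the genuine Day 113 value | 27 | 27 |
| Switch known: total | 69 (83%) | 48 (58%) |
| Switch missing before Month 4: total | 69 − 13 = 56 (67%) | 48 − 13 = 35 (42%) |

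**Example.** Last dose and ET Day 130, follow-up Day 158: Month 4 shows Day 113, Month 6 shows Day 158, and Day 130 appears nowhere.

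**Earlier stops.** At +28, haematology and chemistry follow-up values appear as Month 2 for stops on Days 22–42, Month 3 for Days 43–70, and Month 4 for Days 71–85. At +28 to +42 they displace no further ET value. A follow-up lipid value in the Month 2 window is unused, because lipids are not scheduled there.

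**Completers.** A Month 6 visit on Days 162–176 is at most 7 days from target. Follow-up even 21 days later falls on Day 183 or after, at least 14 days from target, so the Month 6 value is always kept.

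**Later retests.** Remove the follow-up value but add one retest at +56 (an assumption), switch day known. ET is again in no row for L = 114–141, which is 28 of 83 days. With ET on Day 130, the Day 186 retest becomes Month 6 and has the same effect.

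**The case against.** The sponsor can say that off-treatment data are used by design and that Month 6 in Appendix 2 means time since first dose, not treatment status. That stands as far as it goes; the use of off-treatment values is not disputed. What Appendix 2 does not state as intended is that a follow-up test should remove the value at stopping or switch off the rule for early leavers.

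The total also combines two outcomes. On 27 of the days counted, Month 4 correctly shows an on-treatment scheduled value, and only the rest are replacement within a row. That stands, and the table separates them.

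SAP 6.6 refers to sponsor reporting standards that may already separate follow-up. They are not in these documents, and the explicit text of Appendix 2 does not do so.

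A reader might also infer a conflict for placebo subjects who stop before switching. SAP 5.2 says the "treatment label for reporting visits after Month 3 through Month 6 will be" the placebo-to-tofacitinib one, while SAP 4.3 says "Subjects will be classified according to the actual study treatment received". The documents do not establish a conflict. The label names a randomized sequence, SAP 6.6.1 likewise displays adverse events to Month 6 by sequence, and a sequence label does not assert that each subject switched.

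**Conclusion.** The point holds as a minor defect in by-visit laboratory reporting. As written, Appendix 2 can show an off-drug value under a scheduled visit and can leave the Early Termination value out of every by-visit row. It does not do so for the latest stops, from about Day 149 (+42) or Day 156 (+28).

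The figures of 69 and 48 of 83 (56 and 35 with the switch day missing) rest on the timing assumptions above and are shares of stop days. A reader might take them as shares of subjects, but the documents give no stop rate. As an illustration only: if 2% to 5% of 204 subjects stop early with a Follow-up Visit and half of them stop after Month 3, then 204 × 0.02 × 0.5 × 0.42 = 0.9 and 204 × 0.05 × 0.5 × 0.83 = 4.2, so about one to four subjects lose the value.

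A reader might also infer that safety events are hidden or efficacy is biased. Neither follows. The stops still appear in the adverse event and withdrawal summaries (SAP 6.6.1), and the Follow-up Visit collects no efficacy data. The effect is confined to descriptive change from baseline by visit, and to the normal/high/low tables only if these are by visit, which SAP 6.6.2 leaves unclear.

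**What to change.** Add to Appendix 2:
- In by-visit safety displays, laboratory values from the Follow-up Visit and from any later post-treatment retest (values after the Early Termination or Month 6 visit, identified by visit label or flag) are excluded from the scheduled windows and shown in a separate off-treatment Follow-up row.
- Such values do not count as an observation in the Month 6 window for the early-leaver rule.
- Month 6 stays open-ended, so that late visits, including the COVID-delayed assessments allowed by Protocol 7.7, are kept.

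The retests must be covered. Excluding the Follow-up Visit alone restores the Early Termination value on all 83 stop days only if no later retest exists. SAP 6.6.2 should also say whether the normal/high/low tables are by visit.

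The cost is one or two sentences, one programming flag and one table row. Data collection and efficacy analyses do not change. The drawback is that the Follow-up row mixes early stoppers with completers, so it must be labelled as off-treatment. If the sponsor's standards already do this, Appendix 2 need only say so.

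Separately, the protocol's follow-up timings differ and must be reconciled: 28 to 42 days in 6.2.8 and 28 (+14) days in Schedule of Activities footnote 18, against 28 ± 7 days in 6.3, 6.3.2 and 7.5.7.
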